(4) [name]	Professor of Psychiatry and Youth Mental Health
University of Birmingham Birmingham	[contact]
(5) [name]	Chief Scientific Officer
Bravo Victor	[contact]

Study name:	Traumatic brain injury related changes in military veterans				
Protocol version number:	3.0	version date:	11 October 2023	Page:	3 of 22

STUDY SUMMARY

Title

Traumatic brain injury related changes in military veterans

Study Design

Prospective observational pilot study

Objectives

- To evaluate candidate biomarkers in blood and saliva from veterans and non-veterans with traumatic brain injury and correlate these with visual and mental health assessments and patient reported outcome measures.
- To assess mental health status in traumatic brain injured patients and correlate these with changes in patient reported outcomes to assess quality of life over time.
- To relate these changes after traumatic brain injury to understand how quality of life is affected by injury.

Participant Population and Sample Size

Up to 90 subjects

Outcome Measures

- Fluid biomarker levels in blood and saliva including neuronal damage and immune markers.
- Visual function tests including optical coherence tomography, visual field, visual acuity, colour vision, contrast acuity, pupil reactivity, focussing mechanism and eye movement.
- Mental health and quality of life outcomes: social and occupational functioning assessment scale (SOFAS) and self-reported measures such as BIVSS (visual impairments), PHQ-9 (Patient Health Questionnaire; depression), GAD-7 (General Anxiety Disorder), PCL-5 (PTSD checklist for DMS-5), SBQ-R (Suicidal Behaviour Questionnaire Revised), AUDIT (Alcohol Use Disorders Identification Test) and EQ5D5L36 (quality of life).

Key Eligibility Criteria

Inpatient or outpatient care after moderate to severe traumatic brain injury

Intervention

None

Trial Schema

Study name:	Traumatic brain injury related changes in military veterans				
Protocol version number:	3.0	version date:	11 October 2023	Page:	4 of 22

Study name:	Traumatic brain inju	Traumatic brain injury related changes in military veterans					
Protocol version number:	3.0	version date:	11 October 2023	Page:	5 of 22		

TABLE OF CONTENTS

Protocol development and sign off1	
Protocol Contributors	
Name: 1	
[name]	
[name] 1	
[name] 1	
Protocol Amendments	
Amendment number1	
Date of amendment	
Protocol version number	
Type of amendment1	
Summary of amendment1	
CI Signature Page	
Study Name:	

1.1. Background

Traumatic brain injury (TBI) results in disruption of the normal function of the brain caused by blows, bumps or jolts to the head. These injuries can be penetrating or non-penetrating and cause loss of consciousness, impair cognitive function, alter mental state and cause neurological deficits such as muscle weakness and loss of vision. In the most severe form of TBI, the entirety of the brain is affected by diffuse injury and swelling. Treatment modalities vary extensively based on injury severity, ranging from daily cognitive therapy sessions to radical surgery such as bilateral decompressive craniectomies. Psychiatric disorders occur after both mild and severe TBI¹. For example, TBI patients may develop depression after damage to the prefrontal grey matter, dorsolateral prefrontal cortex and left basal ganglia¹⁻⁵. Some TBI patients develop obsessive compulsive disorder after damage to the orbitofrontal cortex, caudate nucleus, and anterior cingulate⁶⁻¹⁰. Others develop post-traumatic stress disorder and post-traumatic amnesia¹¹⁻¹³, psychosis⁵, and personality changes such as apathy¹⁴ and aggression¹⁵. Poor mental health therefore exacerbates the burden of living with TBI, with some indication that mental health problems precede other areas of functional decline¹⁵.

Overlap in brain injury and mental health occurs as cognitive, psychological, emotional and behavioural responses originate in the brain, with both brain injury and mental illness occurring after damage to neuronal pathways. TRACK-TBI found that 1 in 5 individuals went on to experience mental health issues after mild TBI^{15,16} whilst the rates of completed suicide and the relative risk of suicide post-TBI were almost 3 times higher than the general population¹⁶. Increasingly, TBI fluid and imaging biomarkers are being used for their diagnostic, prognostic and predictive value, as an aide to clinical decision making. Fluid biomarkers from peripheral blood or cerebrospinal fluid can diagnose and determine the severity of TBI. For example, the fluid biomarkers glial fibrillary acidic protein (GFAP), S100β, tumor necrosis factor-α and myelin basic protein (MBP) associated with TBI severity¹⁷. Since up to 80% of TBI patients suffer visual disturbances, changes in visual structure and function can be used to diagnose and prognosticate TBI^{18,15}. Therefore, **a better understanding of the neuropsychiatric changes post-TBI**, aided by our collection of biofluids and visual imaging data in military veterans, could inform a larger study to identify potential preventative treatments after TBI but also inform the disease specific and transdiagnostic discovery bioscience with significant and wider impact.

1.2. Study Rationale

1.2.1. Justification for participant population

Military personnel are increasingly at risk of TBI during conflicts and especially exposure to blast. Severe TBI is easy to spot but over 80% of TBIs in military personnel are mild TBI (mTBI), which is characterised by short-term loss of consciousness and or altered mental state. Mild TBI has emerged as a signature injury and an important concern in both US and UK military populations, because of the potential for long term negative sequalae. Of military personnel returning from Iraq and/or Afghanistan, up to 40% of military personnel in the US had a mTBI¹⁹, whilst the prevalence in the UK cohort was smaller at around 5%²⁰ with one report suggesting that neuropsychiatric problems could affect as much as 70% of veterans²¹. However, all severities of TBI are associated with a broad range of subsequent psychiatric and neurological disorders including headache, fatigue, sleep disorder, dizziness, amnesia, information processing slowing, executive dysfunction, depression, anxiety and suicidal behaviour²². TBI sustained in combat is also accompanied by posttraumatic stress disorder (PTSD) and bodily trauma, which adds to the difficulty in determination of the relative contribution of each of these factors to eventual outcomes. Biomarkers have the potential to help identify those at risk of poor recovery which would aid deployment of early interventions.

The aim of this investigation is to evaluate candidate fluid biomarkers in blood and saliva from veterans who have suffered a TBI and correlate these with visual assessments, standard clinical assessments of mental health and patient reported outcome measures (PROMs) that assess mental health and quality of life over time. All of the data will be combined to develop a multifaceted algorithm to predict prognosis in veterans and provide pilot data to inform a larger study. The study will also identify biomarkers that can enable rapid decisions as to whether further intervention is required to prevent significant changes to qualify of life in veterans with a TBI and inform rehabilitation strategies to increase optimal management opportunities.

Study name:	Traumatic brain inju	raumatic brain injury related changes in military veterans					
Protocol version number:	3.0	version date:	11 October 2023	Page:	8 of 22		

1.2.2. Justification for design

This is a prospective observational pilot study. Following 3 groups of participants, including an acute TBI group, a veterans' group with diagnosed TBI and a control group with no previous episodes of brain injury allows us to: (a) assess the changes in fluid and imaging biomarkers and (b) assess mental health status and quality of life over time. Values obtained from levels of biomarkers and measures for mental health status and quality of life will be subtracted from data in the acute TBI and the veteran group. This will reveal changes over time in acute TBI patients who have suffered a TBI and in veterans with TBI. Comparisons between the acute TBI group and the veteran group will then reveal differences between these two groups and whether one group is more susceptible to worse mental health and quality of life status. Since, we will collect longitudinal data, we may be able to tell how long after a TBI do the reported mental health and quality of life problems occur in acute TBI and veterans with a view to developing therapeutic intervention to delay or treat these problems.

We will compare these with the same biomarkers and assessments in control patients (without any episodes of brain injury). This will help us to understand if there is anything different in TBI patients that may tell us who is likely to go onto to develop mental health problems and poorer quality of life outcomes.

Whilst we will aim to perform all investigations at all time points on all patients, not all patients will be able to devote sufficient time and effort to participate and, as this is an exploratory study, we will not exclude patients where they fail to complete all stages of the assessment.

2. Aims, Objectives and Outcome Measures

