4.1. Inclusion Criteria for acute TBI group

- 1. Over the age of 18
- 2. Must have 2 eyes

3. Not all participants will have capacity to consent (e.g. moderate to severe TBI). For these participants, they will require a personal or nominated consultee.

- 4. Willing and able or consented by consultees to follow the protocol
- 5. Moderate or severe head injury requiring admission to the Queen Elizabeth Hospital within the prior 14 days

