4.2. Inclusion Criteria for veterans' group

- 1. Over the age of 18
- 2. Must have 2 eyes
- 3. Capacity to consent
- 4. Willing and able to follow the protocol

5. Moderate or severe head injury requiring admission to a military hospital facility or service personnel with planned departure from the Armed Forces within 6 months.

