4.7. Eligibility criteria for nominated consultee

- 1. Only appointed if no family member or friend is willing or able to act as a consultee
- 2. Must have no connection with the project
- 3. Capacity to consent

5. Consent

A member of the clinical care team (e.g. doctor, research nurse or practitioner) at Queen Elizabeth Hospital Birmingham will first identify potential acute TBI and control group participants to ascertain whether they are interested in participating in the study. They will be approached after either head injury for the acute TBI group (i.e. 0-14 days post-injury) or any other injury not involving the head for the control group in the inpatient ward or in clinic (outpatient) or during telephone / virtual follow up.

Veterans will be recruited through existing links with the military and as they are discharged from military care into NHS care. This includes partner site the Defence Medical Rehabilitation Centre in Stanford Hall where the clinical care team will identify suitable participants and obtain full written consent prior to participants visiting the Queen Elizabeth Hospital in Birmingham for blood/saliva collection and all tests. Veteran's will also be recruited through advertisements and direct contact with veterans' charities such as Bravo Victor and Blind Veterans UK.

Once an acute TBI or control patient or a veteran has expressed an interest in participating, and has provided full written consent to the clinical care team, they will be introduced to a member of research team (e.g. post-doctoral research fellows or assistants). A member of the research team will determine by talking to the patient and review of the patient's notes whether or not the patient is suitable to participate in the study. If the patient is not suitable for inclusion in the trial, their data will not be retained.

In addition, veterans who have already been discharged from the military will also be recruited through advertisements and direct contact with veterans' charities such as Bravo Victor and Blind Veterans UK. These patients will contact the research team if interested and a trained member will obtain full written consent prior to determining the suitability of the participant in the study.

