6.1. Summary of assessments

Figure 2. Assessments planned for acute TBI patients

		TRI	AL PERIOD	
	Enrolment	Initial assessment (may be at enrolment)	Post-allocation (monitoring interval clinically determined)	Close-out
TIMEPOINT**	-t1	Contact 1 (0-14 days post head injury or at enrolment)	Contact 2-5 (1, 3, 6 and 9 months after head injury or enrolment)	Contact 6 (12 months after head injury)
ENROLMENT:				
Eligibility screen	Х			
Informed consent	Х			
ASSESSMENTS:				
Collect blood and saliva		X (face to face)	X (1 and 6 months only, face to face)	X (face to face)
Visual function tests (e.g. visual acuity and field tests, optical coherence tomography (OCT), OCT angiography, pupillometry, Email saccadic latency and autorefraction.		X (face to face)	X (1 and 6 months only, face to face)	X (face to face)
Mental health outcomes (social and occupational functioning assessment)		X (face to face and remotely)	X (1 and 6 months only, face to face and remotely)	X (face to face or remotely)
Self-reported measures collected by post (e.g. BIVSS (visual impairment, General anxiety disorder, PTSD, Suicidal behaviour, alcohol use and quality of life		X (all collected remotely)	X (1, 3, 6 and 9 months, all collected remotely)	X (all collected remotely)
Head injury outcome				х

Study name:	Fraumatic brain injury related changes in military veterans					
Protocol version number:	3.0	version date:	11 October 2023	Page:	13 of 22	

		TRI	AL PERIOD	
	Enrolment	Initial assessment (may be at enrolment)	Post-allocation (monitoring interval clinically determined)	Close-out
TIMEPOINT**	- t 1	Contact 1 (at enrolment)	Contact 2-4 (3, 6 and 9 months enrolment)	Contact 5 (12 months after enrolment)
ENROLMENT:				
Eligibility screen	Х			
Informed consent	Х			
ASSESSMENTS:				
Collect blood and saliva		X (face to face)	X (at 6 months only, face to face)	X (face to face)
Visual function tests (e.g. visual acuity and field tests, optical coherence tomography (OCT), OCT angiography, pupillometry, Email saccadic latency and autorefraction.		X (face to face)	X (at 6 months only, face to face)	X (face to face)
Mental health outcomes (social and occupational functioning assessment)		X (face to face and remotely)	X (at 6 months only, face to face or remotely)	X face to face or remotely)

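### The acute-versus-veteran comparison in section 1.2.2 cannot separate group from time since injury, and onset after TBI cannot be timed prospectively in veterans whose problems predate enrolment

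*Protocol*

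**What the plan says.** Protocol section 1.2.2 draws two conclusions from following the TBI groups. The first is that comparing acute patients with veterans will show "whether one group is more susceptible to worse mental health and quality of life status"; this is stated without qualification. The second is more cautious: because data are longitudinal, "we may be able to tell how long after a TBI do the reported mental health and quality of life problems occur", and the sentence goes on to name both the acute group and the veterans.

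The two groups enter on different terms.

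- **Acute group (section 4.1):** "Moderate or severe head injury requiring admission to the Queen Elizabeth Hospital within the prior 14 days".
- **Veterans (section 4.2):** "Moderate or severe head injury requiring admission to a military hospital facility or service personnel with planned departure from the Armed Forces within 6 months". The only time limit here concerns leaving the Armed Forces, not the injury.
- **Veterans' recruitment (section 5, Consent):** routes include a defence rehabilitation centre, discharge from military into NHS care, and charities. On the last, "veterans who have already been discharged from the military will also be recruited through advertisements and direct contact with veterans' charities".

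The clocks also differ (section 6.1). In Figure 2 the acute schedule starts at "Contact 1 (0-14 days post head injury or at enrolment", and its last contact is 12 months after the head injury. In Figure 3 the veterans' schedule starts at "Contact 1 (at enrolment" and its last contact is 12 months after enrolment.

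Section 12.2 compares Contact 1 with later contacts. It names mixed models and analysis of covariance but does not mention time since injury. The protocol nowhere says that the date of a veteran's injury is recorded.

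**The concern.** The same contact label means different things in the two groups. At the 6-month contact an acute patient is about 6 months from injury. A veteran is 6 months from enrolment, which may be any time after injury. Contact 1 is an early post-injury value in one group and a value at an unspecified later time in the other, so change from Contact 1 differs in meaning too.

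Time since injury matters on the protocol's own account: the first hypothesis in section 2.1 is that mental health conditions develop over time after TBI. A steeper change in the acute group could be early onset or early recovery. A stable, worse score in veterans could be established illness. Either could be read as a difference in susceptibility.

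For onset, a problem already present at a veteran's Contact 1 began before observation started, and one that came and resolved earlier is not seen at all. As the pilot is meant to inform a larger study (section 1.2.1), a misreading could carry forward.

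**Working it through.** **1. The plan's own figures.** There is none for the acute-versus-veteran contrast. Section 12.2 gives 24 complete participants from 30 recruited: 24 / (1 − 0.20) = 30. Three groups give 3 × 30 = 90, which agrees with the Study Summary. The power statement there concerns within-person change in retinal nerve fibre layer thickness and does not bear on this point.

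**2. Overlap of observed time since injury.** Let T be a veteran's months from injury to enrolment. T is not in the protocol; the values below are assumptions.

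- Acute window: 0 to 12 months after injury (sections 4.1 and 6.1, Figure 2).
- Veteran window: T to T + 12 months after injury (section 6.1, Figure 3).
- Overlap = max(0, 12 − T).

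| T (months) | Veteran window | Overlap (months) |
|---|---|---|
| 0.5 | 0.5–12.5 | 11.5 |
| 3 | 3–15 | 9 |
| 6 | 6–18 | 6 |
| 12 | 12–24 | 0 |
| 60 | 60–72 | 0 |
| 120 | 120–132 | 0 |

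These are nominal timings. Section 6.2 allows 10% variation, so the acute window could reach 12 × 1.10 = 13.2 months, which moves the cut-off by 1.2 months.

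**3. Onset.** Suppose a problem starts S months after injury.

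- Acute group: it can be placed between two contacts if S lies within 0–12 months.
- Veterans: it can be placed between two contacts only if S lies between T and T + 12. If S is less than T, follow-up shows only that it began before enrolment. Even the S that is observed cannot be expressed as time after injury unless the injury date is known.

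**4. What a pure time-since-injury shift could look like (illustration).** Take 24 per group, no true group effect, a two-sided 5% test, and an assumed shift of k standard deviations due only to time since injury. The probability of a significant group difference is about Φ(k√(24/2) − 1.96):

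- k = 0.3: Φ(1.039 − 1.96) = 0.18
- k = 0.5: Φ(1.732 − 1.96) = 0.41
- k = 0.8: Φ(2.771 − 1.96) = 0.79

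**5. Can adjustment rescue it? (illustration)** Simulate log time since injury at Contact 1 with 24 per group: acute uniform on 0.1–0.47 months, veterans uniform on an assumed range. With r the correlation of group with log time, the variance inflation for the group effect is 1/(1 − r²).

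| Veterans' range (months) | Median variance inflation | Standard error multiplied by |
|---|---|---|
| 1–12 | 9.7 | √9.7 = 3.1 |
| 6–60 | 23.1 | √23.1 = 4.8 |
| 12–120 | 29.5 | √29.5 = 5.4 |

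This uses Contact 1 only. A model over all contacts would recover some information where the windows overlap. Where they do not, adjustment is extrapolation.

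**The case against.** - **The contrast is peripheral.** It stands in the design rationale. Susceptibility of veterans against acute patients is not among the objectives, the four hypotheses or the primary outcome, and the comparison described in section 12.2 is within person, which needs no shared time origin. This stands and limits the reach of the point. It does not support the unqualified sentence in 1.2.2.
- **Some veterans may be recently injured.** Recruitment from rehabilitation and at discharge from military care could bring injuries less than a year old. This stands. A reader might infer that group and time since injury are almost completely confounded; the documents do not support that, because T is unknown.
- **The onset sentence is hedged, and partly right.** It says only that timing may be possible, and in the acute group it is. A reader might infer that the onset question fails altogether; it fails only for problems in veterans that predate enrolment.
- **A statistical analysis plan may add time since injury as a covariate, and injury dates may be in the medical notes.** Both are possible, and covariate choice is commonly left to that plan. Silence in the protocol does not prove that the date will go uncollected. But an analysis plan cannot create overlap for veterans a year or more from injury.
- **Controls could remove the problem.** They cannot. They have no TBI and hence no time since injury, so subtracting their values does not align the two TBI groups.

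**Conclusion.** The point holds in a limited form. As designed, the acute-versus-veteran comparison cannot separate group from time since injury, so it cannot by itself show which group is more susceptible. On nominal timings the observed windows share nothing for any veteran enrolled 12 months or more after injury, and share 12 − T months for those enrolled sooner. How many veterans fall on each side is neither stated nor controlled, so the degree of confounding is unknown. Prospective onset timing is sound in the acute group over 0–12 months. It is not available for veterans' problems that began before enrolment.

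A reader might go further and say that the comparison measures time since injury and not susceptibility. The documents do not support that: a true group difference may be present in the contrast, but it cannot be told apart from time since injury. The probabilities in step 4 and the inflation factors in step 5 rest on assumed shifts and assumed veteran ranges, and only illustrate what could happen. The within-person analyses and the sample size are not affected.

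**What to change.** 1. Record the date of the index TBI for every veteran at Contact 1, and use time since injury, not contact number alone, in any acute-versus-veteran comparison.
2. In section 1.2.2, limit prospective timing of onset to the acute group and to any veterans enrolled soon after injury.
3. In the same section, replace the susceptibility statement with a descriptive comparison of the two groups. State that group and time since injury are confounded, and make direct contrasts only at overlapping times since injury.

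The cost is one extra data item and a wording change in section 1.2.2. The downside is a narrower claim about veterans. Eligibility and the visit schedule need not change.

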2.1. Hypotheses

- 1) TBI alters the structure of the brain causing the development of mental health conditions with time.
- 2) TBI-induced changes can be detected using fluid and imaging biomarkers.
- 3) TBI-induced changes in biomarkers may identify those at risk of poor recovery and the development of mental health conditions affecting the quality of life.
- 4) Changes in visual structure and function predict mental health and quality of life and associate with TBI-related biomarkers.

